## **5.0 TRIAL MANAGEMENT OF PATIENT RANDOMIZED TO REGULAR AND NO-REGULAR SCREENING**

**5.1 Screening test schedule:** Patients randomized to regular screening will undergo non-invasive testing for CAD according the 2005 National Kidney Foundation Guidelines (Table 1 above).(7) Patients randomized to no-regular screening will not undergo regular non-invasive testing for CAD in the absence of symptoms. Patients in both groups who develop symptoms of angina or an angina equivalent, will be investigated according to the local standard of care which may include the use of non-invasive or invasive cardiac testing. Patients will remain on the pilot trial protocol (i.e. regular or no-regular screening) until death, non-fatal MI, transplantation, permanent removal from the waiting list for any reason, or 24 months after enrolment in the pilot trial.

**5.2 Type of non-invasive cardiac screening test:** The choice of non-invasive test(s) will be according to the existing practice of each transplant center. The National Kidney Foundation guidelines recommend that testing should be done with an exercise or pharmacological stress echocardiographic or nuclear imaging test.(7) The choice of exercise or pharmacological stress is determined by the presence of physical limitations (e.g. osteoarthritis) in transplant candidates. The high prevalence of left ventricular hypertrophy in ESRD patients may also decrease the utility of ECG treadmill testing.(6) The type of test used will be documented in all instances.

**5.3 Investigation and management of an abnormal screening test:** The management of an abnormal screening test including performance of coronary angiography as well as treatment of coronary stenoses will be carried out as per the usual standard of care in individual transplant centers and will not be influenced by the investigators or study personnel in any way. CAD-related medical and surgical interventions will be recorded in both groups.

**5.4 Management of patients who develop clinical symptoms of CAD:** Any patient developing clinical symptoms of CAD (e.g. angina, congestive heart failure, or new arrhythmias) will be evaluated according to the standard of care in individual transplant centers and may include the use of non-invasive cardiac stress testing. Management of symptomatic CAD including revascularization will be according to the standard of care at

the local transplant center. Study personnel will document all surgical and medical interventions for CAD.

### **5.5 Permitted investigations in randomized study patients:**

The use of Myocardial Perfusion Scintigraphy or Dobutamine Stress Echo outside the study protocol will be strongly discouraged except for patients that develop signs or symptoms of active cardiac disease, and any use will be documented. Cardiac investigations (including coronary angiography) required prior to surgery for valvular heart disease are permitted. Although resting echocardiography is not indicated for detection of CAD, these tests are commonly performed in wait-listed patients and are discouraged outside the scenarios shown in Table 4 (below).

**Table 4. Accepted indications for resting echocardiography**

1. To follow progression of moderate or greater stenosis or regurgitant valvular disease
2. To monitor patients with bioprosthetic/mechanical heart valves or valve repair
3. To follow progression of pulmonary hypertension in patients with estimated pulmonary artery pressure (PAP) > 50 mmHg or PAP > 40 mmHg with evidence of right heart failure
4. To monitor left ventricular ejection fraction (LVEF) in patients with LVEF <40%

### **5.6 Other study manoeuvres :**

Other than the use of cardiac screening tests, patient management will be as per the usual standard of care in participating transplant centers. Specific considerations include:

**(a) FREQUENCY OF CLINICAL EVALUATIONS DURING WAIT-LISTING:** There may be variation in the follow-up of wait-listed patients by transplant centers. In both study groups, the frequency and content of clinical re-evaluations will be according to the existing practice of the participating study sites. Such evaluations may include cardiology consultations. Clinical evaluations by the study sites during wait-listing will be recorded in both groups. **(b) USE OF MEDICAL OR BEHAVIOURAL TREATMENTS TO PREVENT CAD EVENTS:** Interventions to prevent cardiovascular disease events including the use of lipid lowering agents, aspirin, and beta-blockers remain controversial due to the lack of definitive evidence regarding efficacy in ESRD patients.(6) Medical treatments will not be specified in the trial but will be documented by study personnel. Similarly behavioural therapies such as participation in weight loss, smoking cessation or healthy heart programs may be used.

**5.7 Methods to protect against contamination:** We will minimize the use of non-invasive CAD screening tests outside of the trial protocol by:

- 1) Informing primary nephrologists and primary care physicians who oversee the care of wait-listed patients about the trial and the need to avoid off-protocol non-invasive CAD screening tests.
- 2) Informing cardiologists affiliated with a dialysis program about the study. Eligible patients under active care of a cardiologist will be discussed to ensure agreement with participation.
- 3) Placing a Study Alert on the patient's dialysis chart.

- 4) Providing of a Wallet Card to patients containing a website with information about the trial.
- 5) Educating patients to advise health care providers of their participation and to share the information in their Wallet Card. Annual communication in the form of a Thank You Card for participation will remind participants of trial responsibilities.

## **6.0 FOLLOW-UP**

During wait-listing, follow-up telephone interviews and chart reviews will be performed every six months, with a final follow up interview at 27 months after enrolment performed in patients who do not undergo transplantation within 24 months of the date of study enrolment.

Patients who undergo transplantation during the first 24 months after enrolment will be followed until three months after the date of transplantation. A chart review will occur at the time of discharge from hospital, and an in person or telephone interview and chart review will be performed 3 months after transplantation.

For the small number of patients who undergo transplantation  $\geq$  24 months after enrolment, the last follow up will be 27 months after the date of enrolment even if the 3 months of post transplant follow up are not possible. A chart review will occur at the time of discharge from hospital, and an in person or telephone interview and chart review will be performed 27 months after enrolment.

## **7.0 TRIAL OUTCOME ASCERTAINMENT**

Standardized Case Report Forms will be used to assess all outcomes and study personnel will undergo formal orientation to these CRFs.

**Primary outcomes:** 1) Protocol adherence: We will define adherence by completion of the expected number of screening tests during follow up. For example, the expected number of screening tests in a diabetic patient who did not develop symptoms would be zero in the no-regular screening group, while the same patient would be expected to completed two annual screening tests if randomized to regular screening. Tests performed for clinical symptoms of CAD will be excluded from the determination of adherence.

Screening tests in patients randomized to the regular screening arm will be arranged by study personnel under direction of the site investigator. The study personnel will advise participants of their screening test and follow up directly with the testing facility to determine completion of the test and obtain test results. Use of cardiac screening tests and the reasons for testing, in both treatment groups will be determined using the following procedure: Patients will be interviewed in person during regular dialysis treatments or via telephone every six months. If an unscheduled test was performed the patient will be asked about the reason for test (i.e. presence of symptoms) and the identity of the organizing physician. We believe telephone interviews are feasible in this relatively healthy cohort of wait-listed patients. Patient interviews will be supplemented by review of the transplant center and dialysis patient chart or with treating physicians as necessary every six months. 2) Enrolment will be determined monthly from the Ottawa Hospital Research Institute (OHRI) which issues the randomization scheme.

3) Consent rate: Each transplant center maintains an up-to-date record of incident and prevalent active wait-listed patients. Eligibility criteria will be abstracted from the transplant center chart to a standardized case report form. The case report form will be completed by the study co-ordinator and will include the estimated time to transplantation as determined by the site investigator.

For incident wait-list patients a monthly listing of newly activated wait-list candidates will be obtained from the transplant center during the enrolment period. Eligible incident patients will be sequentially approached with a target enrolment of up to 8 incident patients in each site. Willingness to enroll in the study will be recorded on each patient's case report form along with the reason for any refusal to consent. The number of incident patients approached to complete enrolment will be determined by review of the case report forms.

Prevalent Patients will be enrolled from the local dialysis population attached to each of pilot study transplant centers. The target number of prevalent patients at each site is 18 but there is no maximum number of prevalent patients that can be enrolled. Consent will be documented as described for incident patients.

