## **2.0 PLAN OF INVESTIGATION**

### **2.1 Trial Objectives**

This pilot trial will determine the feasibility of a multi-center, randomized, parallel group definitive trial.(45) Asymptomatic wait-listed patients will be randomized to routine screening for CAD (i.e. Myocardial Perfusion Scintigraphy (MPS) or Dobutamine Stress Echo (DSE)) as per the current standard of care (Table 1) versus no regular screening during wait-listing. Patients enrolled in the pilot will be included in the definitive trial analysis. The pilot trial will include six Canadian transplant centres. The definitive trial will be conducted in over 20 centers in Canada Australia and New Zealand.

**2.1.1 PRIMARY OUTCOMES:** In line with our primary objectives, the primary outcomes are 1) protocol adherence; 2) enrolment rates and 3) consent rates. A patient will be considered adherent if they were adherent to their allocated screening strategy (regular versus no-regular screening) over the 24 month treatment period. Enrolment rates will be assessed monthly during the six month enrolment period. Consent rates will be defined as the proportion of patients enrolled among eligible patients approached for enrolment and will be defined after completion of the six month enrolment period.

**2.1.2 SECONDARY OUTCOMES:** In this pilot study the secondary clinical outcome is a composite outcome of cardiac death and non-fatal myocardial infarction (i.e. the proposed primary outcome in the definitive trial) and will be adjudicated by a blinded clinical endpoints committee using criteria from the POISE Trial.(46, 47). Total mortality, cardiovascular mortality, non-fatal cardiac arrest, stroke, life-threatening bleeding and major bleeding (ie. the proposed secondary outcomes in the definitive trial) will also be defined and adjudicated as in the POISE Trial.(46, 47).

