## **2.2 Sample Size**

Adherence to screening strategies is of utmost importance to demonstrate separation between the two strategies and fidelity of our interventions. In the pilot trial, a sample size of 144 will produce a 95% confidence interval equal to the sample adherence prevalence plus or minus 5% when the true prevalence of adherent patients is hypothesized to be 90%. Thus, 72 patients will be allocated to each treatment group.

In the definitive trial, randomization of 2500 patients is required to demonstrate that no-regular screening is non-inferior to regular screening, with an absolute increase in the primary outcome of cardiac death and non-fatal MI  $\leq 1\%$  in the no-regular screening arm considered non-inferior.

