#### 4.0 PATIENT RECRUITMENT AND INFORMED CONSENT

We will enroll approximately 24 patients per month during the six month enrolment period for a total sample size of 144 patients. With 6 enrolling centres – this is equal to four patients per month X 6 months. The monthly enrolment rate is informed by the requirement to enroll approximately 70 patients per month in twenty-three centers for 36 months to complete the definitive 2500 patient trial.

We plan to consent 40% of the eligible patients approached to participate in the pilot trial. This 40% target in the pilot trial exceeds the estimated consent rate of 34% required to complete the definitive trial.

We also aim to have 50% of participants undergo transplantation within 24 months of the date of enrolment. This is important to demonstrate the risk of no-regular screening.

This will be achieved by enrolling both incident and prevalent wait-listed patients in the trial. To ensure this objective each site will enrol at least 66% prevalent wait-list patients (i.e. 16/24 patients at a given site should be prevalent patients). The data co-ordinating centre will not provide randomization if the site's enrolment of prevalent patients falls below 66% during the pilot study.

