#### **4.2 Prevalent patient identification and enrolment:**

At least 16/24 patients enrolled in each site will be prevalent patients.

In addition to meeting study inclusion/exclusion criteria, prevalent patients should be under chronic dialysis treatment in a location that is accessible to study co-ordinators (i.e. local patients).

The study co-ordinator should review all patients on the active transplant waiting list with the site PI, and identify eligible potential study participants who reside locally first.

The site PI should discuss eligible patients with the treating cardiologist (if applicable) to 1) confirm the cardiologist's agreement with participation in the trial 2) determine whether the patient meets any of the requirements for screening echocardiography (see Table 4 ). Patients declined for participation by their cardiologist will be considered ineligible.

**4.3 Informed Consent:** A study co-ordinator will approach eligible patients to obtain informed consent.

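### The consent rate depends on whom sites choose to approach, because no order is set for prevalent patients, who are at least two-thirds of the sample

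*Combined protocol and SAP*

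**What the plan says.** Section 2.1.1 makes consent one of three primary outcomes and fixes the denominator: "Consent rates will be defined as the proportion of patients enrolled among eligible patients approached for enrolment". Section 4.0 sets the target and the benchmark: "We plan to consent 40% of the eligible patients approached to participate in the pilot trial", and "This 40% target in the pilot trial exceeds the estimated consent rate of 34% required to complete the definitive trial".

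Section 7.0 treats the two recruitment streams differently.

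- Incident patients: "Eligible incident patients will be sequentially approached with a target enrolment of up to 8 incident patients in each site".
- Prevalent patients: "Prevalent Patients will be enrolled from the local dialysis population attached to each of pilot study transplant centers". A target of 18 per site follows, with no maximum and no order of approach. Consent is to be documented as for incident patients.

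Section 4.2 requires at least 16 of 24 patients per site to be prevalent. The co-ordinator and the site PI go through the whole active list together and "identify eligible potential study participants who reside locally first". That is the only ordering rule for this stream. Section 4.1 has a similar local-first step for incident patients.

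**The concern.** A rate with approached patients as its denominator describes the eligible population only if the approach is complete, consecutive or random. The plan secures this for the smaller stream and leaves it to the site for the larger one. The local-first rule does not close the gap. Section 3.2 already excludes patients dialysed in a non-local unit, and nothing orders the local patients among themselves.

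Selection need not be deliberate. Starting with patients who are well known to staff or easy to reach would be enough if they are also readier to agree. The enrolment target of 24 a month, and the refusal of randomization when a site's prevalent share falls below 66% (section 4.4), both reward quick prevalent recruitment.

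The consent rate is to be analysed on five of the six months of enrolment, in support of the application for the definitive trial (section 9.0). The patients approached earliest are therefore the evidence. Because eligible prevalent patients who were never approached need not be counted, a reader could not tell afterwards whether selection had occurred.

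**Working it through.** **The plan's own figures.** The plan states: "We will enroll approximately 24 patients per month during the six month enrolment period for a total sample size of 144 patients". This reproduces: 24 × 6 = 144, and 4 per month × 6 sites × 6 months = 144. The precision claim in section 2.2 also holds: 1.96 × √(0.9 × 0.1 / 144) = 4.9 points, against the stated 5. The 40% and 34% consent figures cannot be reproduced, because no count of eligible patients is given.

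**What the measure can do if approach is unselected.** At 40% consent, 144 enrolled means 144 / 0.40 = 360 approached, or 60 per site. The 95% half-width is 1.96 × √(0.4 × 0.6 / 360) = 5.1 points. Taking 360 as fixed, the binomial chance of at least 144 consents is 1.0% if true consent is 34% and 0.003% if it is 30%. Under unselected approach, reaching 40% would be informative.

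**What selection in the prevalent stream does.** Assume true consent of 30% in both streams, and that the prevalent patients actually approached consent at 40%. Both figures are assumptions.

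| Mix per site (prevalent/incident) | Prevalent approached | Incident approached | Pooled consent |
|---|---|---|---|
| 16/8 (sections 4.0, 4.2) | 96 / 0.40 = 240 | 48 / 0.30 = 160 | 144 / 400 = 36% |
| 18/6 (section 7.0 prevalent target, 24 in all) | 108 / 0.40 = 270 | 36 / 0.30 = 120 | 144 / 390 = 37% |

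Both results fall short of 40% and exceed 34%. At the 16/8 mix the 95% half-width is 1.96 × √(0.36 × 0.64 / 400) = 4.7 points, giving 31.3% to 40.7%. That interval includes 34% and excludes the assumed true value of 30%. For the pooled rate to reach 40% with incident consent at 30%, the prevalent patients approached would have to consent at 96 / (360 − 160) = 48%.

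**How much selection is needed.** At 40% consent, 16 prevalent enrolments need 16 / 0.40 = 40 approaches per site. The table gives the odds of being approached for a willing patient relative to an unwilling one that produce, on average, 16 consents in 40 approaches (noncentral hypergeometric model).

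| Eligible local prevalent list (assumed) | True consent 30% | True consent 34% |
|---|---|---|
| 233 | 1.7 | 1.4 |
| 120 | 2.0 | 1.5 |
| 80 | 2.6 | 1.8 |
| 60 | 5.9 | 2.6 |

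The 233 is 3500 active patients (section 1.2.1) divided by 15 adult centres (section 1.1). It is a national average before any eligibility or locality limit, so it is an upper guide and not a site count. If a third were eligible (an assumption), the list would be about 78. Suppose such a list splits into halves consenting at 40% and 20%. The more willing half is then 39 patients and yields 39 × 0.40 = 15.6 consents, just under 16. On a list that short, a site could not fill its quota from that half alone.

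**The case against.** The strongest reply is that nothing in the documents says sites will choose patients by willingness, or could predict it. Section 4.2 has the whole active list reviewed, section 4.3 says that eligible patients will be approached, and section 7.0 records eligibility and consent on standard forms for both streams, including reasons for refusal. Section 11.6 mentions a trial manual, not among these documents, that may set an order. The eligible pool could also be small: sections 3.1, 3.2 and 4.2 remove planned living-donor and multi-organ candidates, patients expected to be transplanted within 12 months, patients who need no further screening and patients declined by their cardiologist. Little room for selection might then remain.

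Much of this stands. It limits the size of the effect and rules out any claim that bias will occur. It does not supply an order of approach, and rules on recording consent do not govern who is asked.

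Three stronger readings are tempting but unsupported.

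- A reader might infer that sites stop once they reach a prevalent quota. Section 7.0 sets no prevalent maximum.
- A reader might infer that selection carries the trial to its 40% target. In the illustration only the prevalent stream reaches 40%; the pooled rate is 36% to 37%.
- A reader might infer that adherence is overstated too, because willing patients comply better. The documents give no basis for that link.

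**Conclusion.** The concern holds as a gap in the design of a primary outcome. For at least two-thirds of the sample, the consent denominator is left to site discretion, and the plan requires no record that would reveal selection. The gap permits overstatement; it does not show that any will occur.

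Under the assumed 30% true consent, with 40% among the prevalent patients approached, the pooled rate would be overstated by 6 to 7 points. It would miss the pilot's 40% target but lie above the 34% said to be needed, so a definitive trial short of the required consent could look feasible. The size rests on those assumed rates and on the number of eligible local prevalent patients per site, which is not given. With lists of 120 or more, modest selection is enough; near 60, it would have to be strong.

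**What to change.** In sections 4.2 and 7.0:

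1. At the start of enrolment the data co-ordinating centre puts each site's local active prevalent list in random order, by dialysis unit or shift if visits must be batched.
2. Sites check eligibility and approach patients in that order. Ordering comes before eligibility work-up, so time-to-transplant estimates and cardiologist discussions are needed only for patients reached.
3. Every eligible patient reached in the order counts in the denominator. Eligible patients not approached are logged with the reason.
4. Consent is reported separately for incident and prevalent patients as well as pooled.

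Because the pooled rate depends on the mix, the same edit should reconcile the prevalent figures of 16 of 24 (sections 4.0 and 4.2) and 18 (section 7.0).

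The cost is one generated list per site and slightly less convenient scheduling for co-ordinators. The eligibility forms are already planned, and no extra patients, tests or visits are needed. The change must be made before enrolment, because the order of approach cannot be recovered afterwards.

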### **Secondary Outcomes:**

Ascertainment of secondary outcomes will be enabled by the fact that primary nephrologists and family doctors are required to inform the transplant center of any significant change in the health status of actively wait-listed patients that would impact transplant candidacy. Transplant center charts will be reviewed every six months. Events not reported to the transplant center, will be captured in the direct patient interviews (medical status, health history) and chart reviews (race, gender, medical history, hospitalizations, ER visits, results of Diagnostic Imaging, other test results) conducted every six months during wait-listing (see above). Transplanted patients will have their charts reviewed at time of hospital discharge, and undergo an interview and chart review three months after transplantation. All cases will be recorded on a case report form that conceals treatment group assignment. Case report forms will be reviewed by the primary site investigator, and forwarded to the blinded CEC that will adjudicate outcomes according to the protocol used in the POISE Trial.(46, 47)

